Aims: Specific Aim 1: To measure frequency and timing of transmission of SARS-CoV-2 to household contacts. The proportion of patients and household contacts who have symptoms vs asymptomatic disease will also be measured. Specific Aim 2: To investigate the effect of an intensive infection mitigation intervention (STOPCOV) administered by lay health care workers on the household transmission of SARS-CoV-2, clinical outcomes and psychosocial functioning.
Design: The study design is a type 2 hybrid cluster (household) randomised controlled trial, with outcomes assessed on index patients and their household contacts (Fig 1). 120 consecutively newly diagnosed index patients (GeneXpert SARS-CoV-2 PCR) and up to 8 household contacts will be invited to participate in the trial as part of the prospective observational study evaluating transmission and symptoms. After completing consent, households will be randomised in a 1:1 ratio in blocks of 10 (60 households per group; 360 patient and household contacts per group).
Study setting and population: Klipfontein is a resource-limited, densely populated, high HIV/TB disease burden areas in Cape Town. Newly diagnosed COVID19 cases will be identified from two sources: screening conducted in DTHF mobile screening units and local public sector clinics working closely with DTHF. Consecutive cases (n=120 cases and households) will be invited to participate in the randomised trial and prospective longitudinal follow up of up to ~6 -8 household contacts. The contacts will be followed up after informed consent to SARS-CoV-2 screening, symptomatic questionnaires weekly up to 1 month.
Study size: We will enrol n=120 SARS-CoV-2 positive and n=~6 their household contacts (n=~720).

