Overall Objective: The overarching objective of this protocol is to understand and mitigate household transmission of SARS-CoV-2 infection in a low income, high-density community setting. Data over an 8-month period will be used to determine the Ro for SARS-CoV-2 infection, the rate of symptomatic disease and the impact of a lay health care worker administered infection mitigation intervention (STOPCOV) in low income, high-density communities in South Africa.

Specific Aim 1: To measure frequency and timing of transmission of SARS-CoV-2 to household contacts. The proportion of patients and household contacts who have symptoms vs asymptomatic disease will also be measured.

Specific Aim 1 Endpoints: SARS-CoV-2 transmission will be monitored using nasopharyngeal swabs for SARS-CoV-2 PCR and serology (IgM/IgG) assays in all HHC weekly for 1 month. Symptom checklists will be completed daily and collated weekly for each HHC.

Specific Aim 2: to investigate the effect of an intensive infection mitigation intervention known as STOPCOV administered by lay health care workers, compared with enhanced usual care, on SARS-CoV-2 household transmission.

Specific Aim 2 Primary Endpoint: The proportion of transmissions to HHC in the households of COVID cases assigned to the infection mitigation intervention arm compared with the households in the enhanced usual care (EUC) arm.

Population and Sample: We will consecutively recruit n=120 SARS-CoV-2 positive index patients 12 years and older. The index patients will be identified from referrals from associated public sector clinic screening in a high-density community in Cape Town. Each household is estimated to have 6-8 occupants. We will invite HHC (n=~6-8) household contacts of each of the index patients (n=~720).

Duration: The study will be conducted for eight months from June 2020 and last until Jan 2021.

[figure not shown]

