Setting: The study will be conducted in KMP. The community is a resource-limited, densely populated, high HIV/TB disease burden area in Cape Town. The DTHF Tutu Tester Mobile Clinics offer mobile HIV testing days in various locations in KMP. Specifically, there are four high HIV disease burden communities in the district; Philippi (population n=200,803), Crossroads (n=36,043), Gugulethu (n=98,468) and Nyanga (n=57,996). In addition to our well-established relationship with community organisations such as an independent advisory board, we have provided HIV testing services and linkage to treatment from the mobile clinic since 2008 and are currently partnering with the KMP subdistrict health team in providing COVID screening and testing. Given our long-term relationship with and service in the community, our relationships with the Provincial Department of Health, and our experience with the research platforms, it is feasible for us to successfully execute the proposed

research. The mobile clinic team will provide a screening service and SARS-CoV-2 polymerase chain reaction (PCR) testing with the GeneXpert or courier samples to accredited laboratories and rapid testing with the SARS-CoV-2 antibody COVID-19 IgG/IgM Rapid Test Device. Additionally, the mobile clinic team will offer screening for HIV, TB, STI and chronic diseases (e.g. diabetes, hypertension, and obesity).

Design: A cluster randomised controlled study with longitudinal follow up of SARS-CoV-2 infection in 120 households which have newly diagnosed SARS-CoV-2 positive cases. The index cases and their household contacts will be invited to participate in the study after informed consent. Baseline surveys and screening and then weekly screening of HHC will occur (Table 1). These household contacts will be tested at 0, 1, 2, 3 and 4 weeks.

The study design is a type 2 hybrid cluster (household) randomised controlled trial, with outcomes assessed on index patients and their household contacts (Diag 1). 120 consecutively newly diagnosed index patients (GeneXpert SARS-CoV-2 PCR) and up to 8 household contacts will be invited to participate in the trial as part of the prospective observational study evaluating transmission and symptoms. After completing consent, households will be randomised in a 1:1 ratio in blocks of 10 (60 households per group; 360 patient and household contacts per group).

Diagram 1: Study flow

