Written material	Extensive content available online. Limited content available as pamphlets and WhatsApps. No systematic distribution of WhatsApp messaging.	Printed copies of PACK Home Volume 1 (Be coronavirus safe) and Volume 2 (COVID-19 Caring at home).	Printed copies of PACK Home Volume 1 and 2. WhatsApp optimised versions of content delivered daily.
Community Health Worker visits	Mainly alongside chronic medication delivery.	Mainly alongside chronic medication delivery.	Additional one off household assessment to establish relationship at baseline.
Equipment	Distributed through drives.	Masks and hand sanitiser at enrolment.	Masks, hand sanitiser, bleach, gloves (to wear when using bleach). Plus on demand during follow-up.
Telephonic and text message support	On demand hotline service.	On demand hotline service	Scheduled support: Active phase (until 14 days after last person in household diagnosed): daily.

			Follow-up phase: 3 times a week for 7-14 days. Close-out: 5 days (to facilitate full integration into usual services).
--	--	--	---

* As of 06/07/2020 patients are considered at risk of severe COVID-19 if they are: 55 years or older or of any age with any one of the following: diabetes, on TB treatment, HIV, kidney disease, hypertension, previous TB, chronic lung disease, on cancer treatment.

Outcomes will be independently assessed by research staff who are also collecting biological samples at 0, 1, 2, 3, and 4 weeks. Baseline surveys will collect information on demographics, COVID-19 symptoms, household tracing information and home/ dwelling characteristics that impact transmission (size, rooms, ventilation, access to safe water, laundry facilities). Patient and household contact surveys will also include standardised measures to assess psychosocial functioning: General Health Questionnaire; UCLA Loneliness Scale and a version of the Brief AIDS-Related Stigma scale adapted for COVID-19. Research staff will complete a checklist documenting uptake of infection control measures at all follow-up contacts (1, 2, 3, 4 weeks). A sample size of 120 households (60 per group; 320 patient and household contacts per group) will provide 80-99% power to detect a 40% reduction in R₀ (2.5 to 1.5) varying the intra-cluster correlation efficient from 0.90 (80%) to 0.05 (99%) (Table 3). Index patients and their contacts will be reimbursed with R150 for their time at the baseline and final study visits.

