A mixed methods process evaluation will explore acceptability, feasibility and contextual factors impacting intervention delivery guided by the Consolidated Framework for Implementation Research. Qualitative data collection during the first 4 weeks will be curtailed to minimise exposure of research staff completing qualitative interviews (high risk for COVID-19 transmission) and will be limited to observation of CHW training and up to 5 initial CHW household assessments. We will explore the feasibility of recording and analysing telephone interactions between CHWs and households. Once a household has been determined to be COVID-19 free (2 weeks after last symptoms in a diagnosed person) trained qualitative interviewers will conduct interviews with patients, household contacts and caregivers. These in-depth interviews will be limited to a purposive sample of 5 households per group. CHWs and community leaders will also be interviewed.

Assessing SARS-CoV-2 transmission: The research team will conduct SARS-CoV-2 testing with household contacts at baseline and weekly for 1 month. SARS-CoV-2 transmission will be monitored using nasopharyngeal nostril swabs for SARS-CoV-2 GeneXpert PCR and antibody COVID-19 IgG/IgM Rapid serology assays. Nasopharyngeal samples will be collected in a well-ventilated sputum collection space and staff will have adequate protective equipment. Venepuncture will be used to obtain dried blood spots. The test results will be delivered telephonically to household contacts within 24 hours of the test. HHC will complete a daily symptom checklist and symptom data will be collated weekly by the research team. Six months after a positive SARS-CoV-2 antibody, the study nurse will visit the participant household to conduct SARS-CoV-2 serology to assess for the presence of antibodies.

Eligibility of index case:

Inclusion:

Individual >12 years

Able to give assent if <18 years with parental/guardian consent

Able to give consent > 18 years

Self-isolating at home at the time of COVID diagnosis

Exclusion:

<12 years

Unable to give consent

Eligibility of HHC

Inclusion:

Living in the same household as index case

Able to give assent if 12-17 years with parental/guardian consent

Able to give consent \geq 18 years

Exclusion:

Unable to give consent

Table 2: Study procedures

Study participant	Procedure	Baseline	Week	Week	Week	Week
			1	2	3	4
Index						
	ICF		x			
	Demography survey		x			
	Symptom check	x		x	x	x
	Follow up surveys	x		x		x

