4. STUDY OUTCOMES

4.1. Primary study outcomes

- The incidence rate of SARS-CoV-2 infections among HHC of the index COVID19 cases over a 4 week period
- The time to transmission to HHC during that time period
- The association between the time to transmission and clinical symptoms of the index cases
- The symptomatic/asymptomatic ratio among transmitted SARS-CoV-2 in household contacts
- The proportion of transmissions to HHC in the enrolled households of COVID cases assigned to the infection mitigation intervention arm compared with the households in the enhanced usual care (EUC) arm.

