8. ANALYSIS OF SECONDARY STUDY OUTCOMES

8.1. The proportion of index patients and HHC that were hospitalised for COVID-19 during the period of follow-up in the intervention arm as compared to the enhanced usual care (EUC) arm.

The binary outcome of hospitalisations for COVID-19 will be determined for the different study arms will be compared and analysed using a mixed effect logistic regression model.

8.2. The proportion of deaths in index patients and HHC due to COVID-19 during the period of follow-up in the intervention arm as compared to the enhanced usual care (EUC) arm.

The binary outcome of deaths in index patients and HHC for COVID-19 will be determined for the different study arms and will be compared and analysed using a mixed effect logistic regression model.

8.3. The proportion of index patients and HHC that showed improved psychosocial functioning in the intervention arm as compared to the enhanced usual care (EUC) arm.

The continuous outcome of psychosocial functioning in index patients and HHC for COVID-19 will be compared and analysed using linear regression.

8.4. The association between the time to transmission and clinical symptoms of the index cases

The incidence of transmitted SARS-CoV-2 infections to household contacts will be estimated and compared by the number and duration of clinical symptoms of the index patients. These symptom characteristics can also be included in the frailty models.

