8.5. The symptomatic/asymptomatic ratio among transmitted SARS-CoV-2 in household contacts

The proportion of symptomatic and asymptomatic transmitted SARS-CoV-2 infections will be calculated, overall, with 95% confidence intervals based on binomial or asymptotic normal distributions.

8.6. The incidence of SARS-CoV-2 transmitted to HHC of the index COVID19 cases over a 4 week period, stratified by COVID-19 wave.

The incidence of SARS-CoV-2 will be compared by COVID-19 wave using exponential frailty models and including an indicator of the wave in the model.

The COVID19 wave will be defined as follows:

- wave 1: date of diagnosis of index case between 1 May and 31 November
- wave 2: date of diagnosis of index case from 1 December onwards

8.7. Analysis of household exposure to SARS-CoV-2 at baseline using the baseline serology result, and development of antibodies using the serology result during follow-up.

Longitudinal weekly prevalence profiles of serology results will be summarized overall and by study arm. These profiles can be analysed using hierarchical mixed effect logistic regression models with both household and HHC as nested random effects. Time to development of antibodies can be analysed using exponential frailty models. Models will include baseline serology results.

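### Swabs and symptom checks both end at week 4, and SAP 8.5 sets no minimum observation time, so presymptomatic contacts first positive at week 4 would by default count as asymptomatic

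*SAP*

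**What the plan says.** **Testing.** Protocol, Design: "These household contacts will be tested at 0, 1, 2, 3 and 4 weeks".

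**Symptoms.** Protocol, Specific Aim 1 Endpoints: "Symptom checklists will be completed daily and collated weekly for each HHC". The TRaCE Schema (Study setting and population) gives the duration: "The contacts will be followed up after informed consent to SARS-CoV-2 screening, symptomatic questionnaires weekly up to 1 month". Swabs and symptom observation therefore stop together.

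**Later contact.** The only later study visit is in the Protocol under Assessing SARS-CoV-2 transmission: "Six months after a positive SARS-CoV-2 antibody, the study nurse will visit the participant household to conduct SARS-CoV-2 serology". No symptom recall is mentioned there. In Protocol Table 1, STOPCOV telephone and text support may run longer: "Active phase (until 14 days after last person in household diagnosed): daily". That applies to the intervention arm only and is not described as outcome data.

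**Analysis.** SAP 8.5: "The proportion of symptomatic and asymptomatic transmitted SARS-CoV-2 infections will be calculated, overall, with 95% confidence intervals". It defines neither category and gives no observation window, no undetermined category and no sensitivity analysis.

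**Status.** SAP 4.1 lists "The symptomatic/asymptomatic ratio among transmitted SARS-CoV-2 in household contacts" among the primary outcomes, but its analysis stands under "8. ANALYSIS OF SECONDARY STUDY OUTCOMES".

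**The concern.** A contact first PCR-positive at week 2 has 14 further days of daily checklists, one first positive at week 3 has 7, and one first positive at week 4 has none. In a two-way split of all transmitted infections, a week-4 contact who is infected but not yet ill has only one place to go by default: asymptomatic. The missing-data rule in SAP section 5 does not prevent this, because a contact with every checklist complete to week 4 has nothing missing.

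At stake is the answer to the Protocol's Question 2, the burden of symptomatic versus asymptomatic infection. As 8.5 stands, asymptomatic infection cannot be told apart from infection seen too early.

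**Working it through.** **Planning figures.** The documents give no precision or sample size for this ratio. Their only calculation is the power table (SAP Table 1). As a check on the inputs, its cell for R0 2.5 to 1.5 at ICC 0.90 reproduces with 360 subjects per arm, 6 per household and an assumed two-sided 5% test. The effective n is 360/(1 + 5 × 0.90) = 65.5 per arm. With rates 0.208 and 0.125, Φ(0.0833/√((0.208² + 0.125²)/65.5) − 1.96) = 0.7925, against 0.792745 printed.

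**Step 1: share first positive at week 4.** SAP 7.1 uses an exponential (constant-hazard) model. With 4-week incidence p, weekly survival is s = (1 − p)^(1/4), and the share first positive in week k is s^(k−1)(1 − s)/p.
- p = 0.208: 27.2%, 25.7%, 24.2% and 22.9% for weeks 1 to 4.
- p = 0.125: 26.3%, 25.4%, 24.6% and 23.8%.
- For p from 0.075 to 0.417, the week-4 share runs from 24% to 20%.

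**Step 2: how many of those are still presymptomatic.** This needs values that the documents do not give. Assumed: lognormal incubation with log-SD 0.42; PCR positive from 0, 2 or 3 days after infection; infection times either even over 28 days (the low-incidence limit of constant hazard) or early, with a one-week half-life. Percentages refer to eventually symptomatic contacts, and ranges run over the three PCR delays.

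| Median incubation | Infection times | First positive at week 4 | Onset after day 28, week-4 positives | Onset after day 28, week-3 positives | Relative understatement | True 0.50 reads |
|---|---|---|---|---|---|---|
| 3 days | even | 25-28% | 10-46% | under 1% | 3-12% | 0.44-0.49 |
| 3 days | early | 7-9% | 8-40% | under 1% | 1-3% | 0.49-0.50 |
| 5 days | even | 25-28% | 35-72% | 1-6% | 10-20% | 0.40-0.45 |
| 5 days | early | 7-9% | 30-67% | 1-5% | 3-5% | 0.47-0.49 |
| 7 days | even | 25-28% | 58-87% | 7-20% | 19-27% | 0.36-0.41 |
| 7 days | early | 7-9% | 54-84% | 7-18% | 6-9% | 0.46-0.47 |

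Using the week shares for p = 0.208 instead of even times moves the upper 5-day figure only a little: 0.229 × 0.719 + 0.242 × 0.061 = 0.18, against 0.195.

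**Step 3: which denominator repairs it.** Take 240 infections (60 × 2.5 + 60 × 1.5), 60 per week, true share 0.50, 5-day median incubation and no PCR delay. Each week has 30 eventually symptomatic contacts. Week 3 loses 30 × 0.061 = 1.8 and week 4 loses 30 × 0.719 = 21.6.
- All infections, as in 8.5: (120 − 1.8 − 21.6)/240 = 0.40.
- Dropping only symptom-free week-4 positives: the 8.4 already symptomatic stay, so (88.2 + 8.4)/(180 + 8.4) = 0.51. This is above 0.50 because the rule selects on the outcome.
- Dropping all week-4 positives: 88.2/180 = 0.49. The remaining shortfall is the week-3 loss.

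**Step 4: cost in precision.** By week 3: 150 × (1 − 0.229) + 90 × (1 − 0.238) = 184 infections. By week 2: 150 × 0.529 + 90 × 0.517 = 126. The half-width at a proportion of 0.5, ignoring clustering, is 0.98/√n: 6.3 points for 240, 7.2 for 184 and 8.7 for 126. The share removed at week 4 is (240 − 184)/240 = 23%. If 0.208 and 0.125 are instead applied to 360 subjects per arm, there are 75 + 45 = 120 infections and each half-width is √2 times larger (8.9, 10.2 and 12.4 points).

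**The case against.** Several stronger readings are tempting, and the documents do not support them.

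- **That the SAP directs late positives to be called asymptomatic.** It does not. 8.5 leaves the rule undefined, and the misclassification is what a two-category split gives by default.
- **That the last visits in general are affected.** The effect arises almost entirely at week 4. With a 5-day median incubation, 1-6% of eventually symptomatic week-3 positives have onset after day 28. Making week 2 the main cut-off would discard more infections than this justifies.
- **That the error always overstates asymptomatic infection.** This holds for truncation alone. 8.5 does not tie symptoms to the infection, so unrelated entries on a daily checklist can push the ratio the other way.
- **That Table 1 concedes the point.** The 14-day active phase is support in one arm and says nothing about presymptomatic detection.
- **That the treatment comparison is biased.** 8.5 calculates the ratio overall, with no arm contrast and no test.

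Two further points reduce the size. SAP 7.1 dates infection by first positive PCR or serology, and contacts first detected by serology were probably infected earlier. Read literally, 7.1 also admits contacts who are PCR-positive but seronegative at baseline, who have four weeks of observation. If 30% were detected there (an assumption), the week-4 share at p = 0.208 would fall to 0.70 × 22.9% = 16%.

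What stands after all this is that observation ends with the last swab and 8.5 has no rule for it.

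**Conclusion.** The point holds as a cheap improvement. Followed as written, with the default classification, SAP 8.5 gives a truncated estimate, and truncation by itself understates the symptomatic share. With a 5-day median incubation the understatement is about 3-5% relative if transmission is early and 10-20% under constant hazard; the full range is about 1-27%. These sizes rest on outside assumptions about incubation, PCR timing and the spread of infection times, so only the mechanism is established by the documents. At the upper 5-day values the shift (0.50 reading 0.40) exceeds the 6.3-point sampling half-width; with early transmission it is smaller than that half-width.

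**What to change.** In SAP 8.5:

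1. Define symptomatic, asymptomatic and not yet determined.
2. Calculate the main ratio among contacts first positive at or before week 3, who have at least 7 further days of the daily checklist. Exclude all week-4 first positives whatever their symptoms, because dropping only the symptom-free ones biases the share upwards.
3. Report symptom-free week-4 first positives separately as not yet determined.
4. Give the all-infections ratio alongside, described as a lower bound on the symptomatic share with respect to truncation only.
5. Add a sensitivity analysis limited to contacts first positive by week 2. It matters most if incubation is long: at a 7-day median, 7-20% of eventually symptomatic week-3 positives would still have onset after day 28.

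Also reconcile the primary listing in SAP 4.1 with the secondary heading of section 8. The SAP's list of data sources names symptoms only in the baseline survey, so it should also name the dated daily checklist.

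**Cost.** SAP wording only, before sign-off and database lock, using checklists that the Protocol already collects. About 23% of infections leave the main denominator under constant hazard, and the half-width goes from about 6.3 to 7.2 points (8.7 in the week-2 analysis), before clustering.

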direct contact details (telephone, address, e-mail) will be made available on the informed consent forms. The Site Investigator or designee will maintain, and store securely, complete, accurate, and current study records throughout the study, in accordance with local regulations. All records will be stored confidentially for five years from the beginning of the study.

Overall Risk – The greatest risks here are exposure of staff or among potential participants to undiagnosed cases of COVID and or TB (which may mimic COVID symptoms). Every effort will be made to enhance and adequately implement infection control measures.

Risks to participants: COVID-19 diagnosis has the potential to be stigmatized in communities. Although the study site will make every effort to protect participant privacy and confidentiality, including conducting testing and counselling in a private space, it is possible that participants' involvement in the study could become known to others. Social harms will be monitored and documented throughout the duration of the study. Should additional support be required for some participants due to study-related harms, referrals will be made to community-based services as needed. DTHF has worked in the setting of HIV and TB for 20 years. The staff and policies are well developed to mitigate risk related to stigmatization. The DTHF mobiles for this reason conduct health screening that is multi-disease related with an emphasis on wellness. The mobile units, known as 'Tutu Testers' are a loved brand and well known in communities. Confidentiality is highly regarded and carefully maintained. Good participatory practices are also carefully followed by all. Risk and benefits will be carefully conveyed at the time of recruitment and enrolment. Cases and household contacts will participate voluntarily and can withdraw at any time. All data will be treated confidentially and after consent, participants will be assigned participant identifiers for all study related documents. Study related impacts and harms will be solicited weekly and where necessary participants will be referred for support.

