Overview

A cluster randomised controlled study with longitudinal follow up of SARS-CoV-2 infection in 120 households which have newly diagnosed positive cases. The index cases and their HHC will be invited and enrolled after informed consent. Baseline surveys and SARs-CoV-2 screening (PCR and IgM/IgG serology) and then weekly SARs-CoV-2 screening (PCR and serology) of HHC will occur at 0, 1, 2, 3 and 4 weeks. The households will be randomized to an intensified COVID19 infection mitigation intervention (n=60) administered by CHWs vs the standard messaging (n=60). Please see Figure 1 for a schematic overview of the study design.

EUC = enhanced usual care

Figure 1: Flow chart and schematic overview of the study design.

Sample Size Determination

We calculated the different effect sizes (Table 1). Based on exponential test for comparing hazards, assuming $120*6=720$ subjects, different intraclass correlation coefficients (ICCs) and comparing $R_0=2.5$ (with resulting incidence of 0.208 among 720 subjects) to a reduced R_0 of 0.9 (64% reduction, with resulting incidence of 0.075 among 720 subjects) or 1.25 (50% reduction) or 1.5 (40% reduction).

Table 1: ICC calculations

ICC	R0 2.5 to 0.9	R0 2.5 to 1.25	R0 2.5 to 1.5
	64% reduction	50% reduction	40% reduction
0.05	1.00000	1.00000	0.999944
0.25	1.00000	0.999891	0.991312
0.50	0.999993	0.995042	0.935880
0.75	0.999729	0.972942	0.846222
0.90	0.999033	0.951485	0.792745

Randomization and stratification

After completing consent, households will be randomised in a 1:1 ratio in blocks of 10 (60 households per group; 360 patient and household contacts per group).

Overview of data and data sources for analysis

All data are collected with two individual identifiers: study ID and PID (Western Cape Government health number). The exception is data source #4, which only uses PID.

1. Redcap database
 - a. Baseline survey of index patient and household characteristics (demographics, COVID-19 symptoms, household tracing information, home/dwelling characteristics that impact transmission (size, rooms, ventilation, access to safe water, laundry facilities))
 - b. Uptake of infection control measures at all follow-up contacts (assessment of use of isolation measures and cleaning of household surfaces up to 10 days post case of last diagnosis in household, at 1, 2, 3, 4 weeks).

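### SAP 8.5 reports the symptomatic/asymptomatic split as a plain proportion, with no symptom window, no comparison with uninfected contacts and no allowance for household clustering

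*SAP*

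**What the plan says.** SAP 4.1 lists among the primary outcomes "The symptomatic/asymptomatic ratio among transmitted SARS-CoV-2 in household contacts". Its analysis sits in SAP 8.5, under the secondary outcomes: "The proportion of symptomatic and asymptomatic transmitted SARS-CoV-2 infections will be calculated, overall", "with 95% confidence intervals based on binomial or asymptotic normal distributions". The section gives no symptom list, threshold, time window, rule for symptoms already present at baseline, or comparator.

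The Protocol collects symptoms from every contact, infected or not. Under Specific Aim 1 Endpoints: "Symptom checklists will be completed daily and collated weekly for each HHC". Under Assessing SARS-CoV-2 transmission: "HHC will complete a daily symptom checklist and symptom data will be collated weekly by the research team". Testing follows a fixed schedule: "These household contacts will be tested at 0, 1, 2, 3 and 4 weeks".

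The SAP's list of data sources mentions symptoms only in the baseline survey: "Baseline survey of index patient and household characteristics (demographics, COVID-19 symptoms, household tracing information". The daily checklist is not named there.

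Infection itself is defined in SAP 7.1 by PCR or serology, without reference to symptoms. The incidence interval in 7.1 is adjusted for clustering by household; the interval in 8.5 is not.

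**The concern.** How much infection is silent in this setting is one of the three study questions in the Protocol schema. Because infection is defined by laboratory tests alone, symptom status is a separate classification and needs its own rule. Whatever window is chosen, some infected contacts will report symptoms that have another cause, and a plain proportion counts them as symptomatic infections. The Protocol recognises one such cause under Overall Risk, where it refers to "undiagnosed cases of COVID and or TB (which may mimic COVID symptoms", and it places the study in an area with a high HIV and TB burden.

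Contacts who stay negative fill in the same checklists over the same weeks, so the data to estimate the background are already planned. No analysis uses them. A larger sample would not remove this error, and the planned interval does not reflect it. That interval also treats infected members of one household as independent.

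**Working it through.** The documents state no symptomatic share, background rate or precision for this outcome, so there is no figure to reproduce. The calculations below are illustrations.

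**Inputs**
- p, the true symptomatic share among infected contacts: assumed 40% or 60%.
- b, the proportion with a background symptom in the window: assumed 10-30%.
- Number infected: the sample-size section gives 0.208 × 720 ≈ 150, leaving 720 - 150 = 570 uninfected. The 0.208 equals 60 × 2.5/720. If all 120 households are counted at 2.5 each, there would be 300 infections.

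**Step 1: background symptoms alone.** Assume that any symptom in the window counts and that background symptoms are independent of infection. Then observed symptomatic share = p + (1 - p)b, and observed asymptomatic share = (1 - p)(1 - b).

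| b | p = 40%: observed | ratio (true 0.67) | p = 60%: observed | ratio (true 1.50) |
|---|---|---|---|---|
| 10% | 46% | 0.85 | 64% | 1.78 |
| 20% | 52% | 1.08 | 68% | 2.13 |
| 30% | 58% | 1.38 | 72% | 2.57 |

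**Step 2: dependence on the window.** With an assumed weekly background probability w, four weeks give b = 1 - (1 - w)^4. For w = 5%, b = 1 - 0.95^4 = 18.5%. A true asymptomatic share of 40% then reads 0.40 × 0.815 = 32.6% over four weeks, but 0.40 × 0.95 = 38.0% over one week.

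**Step 3: comparison with the planned interval.** At a 40% asymptomatic share and 150 infections, the 95% half-width is 1.96 × √(0.4 × 0.6/150) = 7.8 points, ignoring clustering. With 300 infections it is 5.5 points. The shifts in step 2 are 7.4 points (four weeks) and 2.0 points (one week).

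**Step 4: the opposing error.** Let A be the true asymptomatic share and t the fraction of truly symptomatic infections with no such symptom recorded, for example because they were detected late. Observed asymptomatic share = [A + (1 - A)t](1 - b). With A = 40%, t = 20% and b = 18.5%, this is (0.40 + 0.12) × 0.815 = 42.4%, an overstatement. The errors cancel at t = Ab/[(1 - A)(1 - b)] = 0.074/0.489 = 15%.

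**Step 5: the correction.** Adjusted share = (observed - b)/(1 - b). For p = 40%: (0.46 - 0.10)/0.90 = 0.40 and (0.58 - 0.30)/0.70 = 0.40. It removes the background error only, not the one in step 4.

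**Step 6: its price in precision.** Take observed 52% of 150 and b = 20% of 570. The crude half-width is 1.96 × √(0.52 × 0.48/150) = 8.0 points. By the delta method, the variance of the adjusted share is (1/0.8)² × 0.001664 + (0.48/0.64)² × 0.000281 = 0.00276. The half-width is 1.96 × √0.00276 = 10.3 points, again ignoring clustering.

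**The case against.** A reader might infer that the SAP counts any symptom over the whole four weeks as COVID-19, and that the asymptomatic share is therefore understated. The documents support neither step. SAP 8.5 is silent on definition and window. The SAP is to be read with the case report forms and the data management plan, which are not available here and may hold symptom items or coding. Step 4 shows that late detection or under-reporting can cancel or reverse the background effect. This objection stands in full.

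The size also rests on an assumed b, and a narrow window or a specific symptom list would make it small. The remark about TB concerns exposure risk; it shows that mimicry is recognised, not how often contacts have such symptoms. These points stand too.

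Always-negative contacts are not a perfect control. Results are telephoned to contacts within 24 hours, so reporting may differ by result. A window tied closely to the first positive test could miss true symptoms when infection is first found by serology. These are reasons to treat the adjusted share as a sensitivity analysis, not to omit it.

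Finally, the outcome is descriptive, its primary status is ambiguous, and the comparison of arms in SAP 7.2 is untouched. That limits the severity. It does not answer the central point: an uncorrected proportion absorbs background symptoms under any window, and the data to gauge them will already be collected.

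**Conclusion.** The concern holds as a gap in the analysis, not as a demonstrated bias in one direction. Certain from the documents: for an outcome listed as primary, SAP 8.5 sets no symptom definition or window, makes no comparison with uninfected contacts, and uses an interval without the household adjustment found in 7.1. Conditional: background symptoms alone would lower the asymptomatic share by the factor (1 - b), which at an assumed b of 10-30% moves a true symptomatic share of 40% across the halfway mark once b reaches 20%. This assumes an any-symptom rule and background symptoms independent of infection. Not established: the value of b, the net direction of error, and the effect of clustering, since the documents give no intraclass correlation for symptom status. The remedy is a cheap improvement.

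**What to change.** In SAP 8.5, before database lock:

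1. Name the daily checklist as the data source, and add it to the SAP's list of data sources.
2. Define a symptomatic infection and fix a symptom window that reaches far enough before the first positive test to cover infections first detected by serology.
3. State how symptoms present at baseline are handled, and how infections first detected at week 4 are handled, given that no later visit in the four-week follow-up can capture their symptoms.
4. Keep the crude share. Beside it, report b among contacts negative on all tests, over windows matched on length and study week.
5. Report (observed - b)/(1 - b) as a sensitivity analysis.
6. Give all shares household-clustered intervals, for example from a bootstrap that resamples households.

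The cost is SAP wording and a small extra analysis of data already planned. The SAP should state the downsides: a wider interval for the adjusted share; the assumption that background symptoms are independent of infection; a b that is too high if some negative contacts are missed infections; and possible differential reporting because contacts are told their results.
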